5.8. Randomization Procedure

All included subjects that meet the inclusion and exclusion criteria will be randomized to one of two treatment groups. Randomization will be centralized using Medidata RAVE and stratified based on wound type (VLU or DFU).

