7.2.2. Dressing changes between site visits

If the wound requires frequent dressing changes (more than once scheduled visit per week), unscheduled visits at the site can be scheduled for dressing changes.

The dressing change can also take place at the subjects home by the subject or by a homecare nurse. The subject will be provided with the additional study products to which he/she is allocated at each visit to use at home in case of additional dressing changes in between visits. An information sheet for the homecare nurse will be distributed to the subjects to be shared with the homecare nurse, providing information about the study and the study treatment to ensure that the protocol is followed between scheduled visits.

In the event of a completed dressing change between the weekly scheduled visits, it must be documented at the next scheduled weekly visit in the eCRF to capture the total number of dressings since last scheduled visit. The subject will be instructed to complete a sheet for dressing changes between the scheduled weekly site visits capturing the dressing change and date of the event.

No clinical investigation-related wound assessments are conducted during the unscheduled visits and/or dressing changes at the subjects home. Cleansing of wound must be done according to standard of care and debridement, if needed. The dressing applications between weekly scheduled visits must be according to randomization.

The total number of dressings, the sizes of the dressings used and frequency of dressing changes per subject is part of the cost-effectiveness analysis.

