Analysis of the primary endpoint:

The percent wound area reduction (WAR) will be analyzed by an analysis of variance with treatment and wound type (VLU and DFU) as fixed effects and wound area at baseline as covariate.

The mean WAR for each treatment group will be estimated together with the 95% confidence interval. Further, the difference in mean including a 95% confidence interval between the 2 treatments will be estimated.

Analysis of the secondary endpoint:

The secondary endpoint, total cost, will be calculated as the number of products used during the investigational period multiplied by the unit price of the product. Unit price will be extracted from Drug Tarif on the date of Last Patient Out.

This secondary endpoint will be analyzed by comparing the mean cost in the two groups assuming the cost data to be normally distributed. It will be tested on a 2-sided 5% test level if the difference in mean between the two treatments is zero. Further, the mean cost for each treatment will be estimated together with a 95% confidence interval.

Analysis of exploratory endpoints:

Percentage wound depth reduction will be analyzed by the same model as described for the primary endpoint but with wound depth at baseline as covariate.

Similarly, the two endpoints related to EQ-5D-5L (the index score and the VAS score) will be analyzed by an analysis of variance with treatment as a fixed effect and the baseline measure as covariate.

The two endpoints; responder defined as a subject reaching ≥ 30% wound area reduction within the 4-week investigation period (Yes/No) and wound healed during the investigation period (Yes/No) will be analyzed by a logistic regression model with treatment and wound type (VLU or DFU) as fixed effects and wound area at baseline as covariate.

Analysis of safety endpoints:

Adverse events will be listed and summarized, if relevant. Device deficiencies and concomitant medication will be listed.

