10.4. Pass/fail criteria

The purpose of this investigation is fulfilled if the performance of the products in the two arms is comparable in terms of wound area, while the mean total cost for Biatain® Silicone is significantly lower than for Standard of Care.

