- may be used on patients who are in treatment for a local or systemic infection at the discretion of a health care professional is suitable for use in combination with compression theraps

The product consists of:

- a vapour permeable top film which is bacteria- and waterproof a lock away layer
- an absorbent polyurethane foam a perforated silicone adhesive
- burguoise protective films

If for experience a suspected allergic reaction or any other side effects, please contact four health care professional.

Sterilised using eth/lene oxide (EO).

Coloplast accepts no liability for any injury or loss that may arise if this product is used in a manner contrary to Coloplastis current

Special storage conditions Keep away from sunlight.

How to use

Preparation

Cleanse the wound and periwound skin in accordance with local guidelines, e.g. lukewarm water or physiological saline solution.

Gently dry the periwound skin.

If any film, cream, cintment or similar product is used, allow the periwound skin to dry before applying the product.

Select a product where the foam overlaps the wound edge by approximately 1-2 centimetres.

Open the pouch and pick up the product from the packaging.

Use the protective films to avoid touching the adhesive side and to ensure aseptic application.

Remove the center protective film.

[figure not shown]

Apply the achesive side towards the wound.

Remove the remaining protective films, one at a time.

Gently run your fingers around the edge of the product to ensure an even and smooth fit to the skin.

Instructions for use

Please read the following instructions carefully.

IFU Master Biatain Silicone Version 2

The Coloplast logo is a registered trademark of Coloplast A/S. All rights reserved.® 2021-08-31

Intended purpose

The product is intended for moist wound healing and exudate management.

The product is intended to be used by health care professionals and patients under the supervision of health care professionals.

Indications

- is indicated for a wide range of low to highly exuding wounds. This includes acute wounds such as donor sites, post operative wounds and traumatic wounds; and chronic wounds such as leg uicers, pressure ulcers and non-infected diabetic foot ulcers may be used to prevent post-operative blistering.

Warnings

Do not re-use the single use product as cross contamination may occur, potentially leading to infection.

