Appendix 2: Instruction for Use Mepilex® Border

(14)

Mepilex® Border EM

Self-adherent soft silicone foam dressing

Do not reuse. If reused performance of the product may deteriorate, cross contamination may occur.

Sterile. Do not use if sterile barrier is damaged or opened prior to use. Do not re-sterilise.

Product description

Mepilex Border EM is a self-adherent, absorbent dressing that maintains a moist wound environment. The waterproof outer layer protects the wound from dirt and bacteria. The dressing has a Safetac® wound contact layer that is a unique adhesive technology. It minimises pain to patients and trauma to wound and skin at dressing removal.

Mepilex Border EM consists of:

- a wound contact layer consisting of soft silicone adhesive (Safetac) and a film carrier
- a flexible absorbent pad in two layers: a foam and a non-woven spreading layer
- an outer film which is breathable but waterproof, providing a barrier to external contaminants

Dressing material content:

Silicone, polyurethane, polyacrylate, viscose, polyester and polyolefin.

Indications for use

Meplex Border EM is designed for the management of a wide range of non/low exuding wounds, such as leg and foot ulcers, pressure ulcers, surgical wounds and traumatic wounds e.g. abrasions, blisters and skin tears.

Mepilex Border EM can also be used as protection of compromised and/or fragile skin

Precautions

- Do not use on patient with known hypersensitivity to the dressing or its ingoing materials.
- Do not use together with oxidising agents such as hypochlorite solutions or hydrogen perceide.
- If you see signs of clinical infection e.g. fever or the wound or surrounding skin becoming red, warm or swollen, consult a health care professional for appropriate treatment.

Instructions for use

Mepilex Border EM may be used by lay persons under supervision of health care professionals.

- Cleanse the wound according to clinical practice. Dry the surrounding skin thoroughly.
- Select an appropriate dressing size/shape. The wound pad should cover the dry surrounding skin by at least 1-2cm.
- 3. Remove the lirst release film and apply the adherent side to the wound.
- 4. Remove the remaining release film(s) and smooth down the border on the skin.

 Do not stretch the dressing.

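### The cost test, the only success condition tied to significance, leaves out the randomisation stratum and baseline wound area; adding both needs no new data

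*Combined protocol and SAP*

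**What the plan says.** - **Cost analysis (section 10.1, secondary endpoint).** Cost is "analyzed by comparing the mean cost in the two groups assuming the cost data to be normally distributed". The null of zero difference is tested two-sided at 5%. No covariate is named.
- **Success (section 10.4).** The trial succeeds only if "the mean total cost for Biatain® Silicone is significantly lower than for Standard of Care". The wound-area condition asks for comparability, with no test or margin.
- **Randomisation (section 5.8).** It is "stratified based on wound type (VLU or DFU").
- **Other models in section 10.1.** The primary model has "treatment and wound type (VLU and DFU) as fixed effects and wound area at baseline as covariate". The depth model replaces area with baseline depth. The responder and healing models use the same terms as the primary. The two EQ-5D-5L models use "an analysis of variance with treatment as a fixed effect and the baseline measure as covariate", so they also omit wound type.
- **Link to cost.** Section 7.2.2 says that "the sizes of the dressings used and frequency of dressing changes per subject is part of the cost-effectiveness analysis". Appendix 1 instructs: "Select a product where the foam overlaps the wound edge by approximately 1-2 centimetres". Appendix 2 says: "The wound pad should cover the dry surrounding skin by at least 1-2cm". Appendix 3 asks for a 1 cm margin of AQUACEL around the wound.
- **Availability.** Wound type and wound size are both recorded at V1 (sections 5.6 and 7.2).

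**The concern.** Stratifying by wound type balances the arms on it and so removes its contribution to the true variance of the treatment difference. A two-sample comparison that ignores the stratum leaves that contribution in the estimated standard error. The interval is then too wide and the test rejects too rarely, to the extent that wound type predicts cost.

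Baseline area is different. It is not a stratification factor, so leaving it out does not distort the type I error, but its share of the cost variance stays in the residual and lowers power.

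Both links are plausible from the documents. Dressing size follows wound size. AQUACEL is supplied only as 5 x 5 and 10 x 10 cm (section 4.8); with a 1 cm margin on each side these cover wounds of about 5 − 2 = 3 cm and 10 − 2 = 8 cm, while eligible wounds run from 1.0 cm in diameter up to 10 x 10 cm. For wound type the evidence is weaker. Section 5.1 says healing patterns differ by type, and section 7.3 says a healed wound needs no further dressing application. Against that, section 4.7 gives one expected change frequency for all subjects.

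What is at stake is a missed saving on the one success condition that is judged by a significance test.

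**Working it through.** **Inputs.** From the plan: two-sided 5%; 40 completers per arm (section 10.2), and 80/(1 − 0.20) = 100 enrolled, so 50 per arm; 1–3 changes a week for 4 weeks (section 4.7). The plan states no power or precision for cost (section 10.2 concerns wound area reduction only), so there is no cost figure to reproduce. Assumed, because the plan is silent: gap g in mean cost between wound types of 0.25–1.5 within-type SD, 50:50 type mix, permuted blocks of 4 within type, normal errors, and baseline area explaining 10–30% of cost variance.

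**Reading the effect scale.** 1–3 changes a week over 4 weeks is 4–12 changes. A uniform spread has mean 8 and SD 8/√12 = 2.31, so a CV of 0.29. At an assumed cost CV of 0.3–0.6, differences of 0.5, 0.75 and 1.0 SD are cost differences of 15–30%, 22–45% and 30–60%.

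**Wound type, closed form.** With a 50:50 mix the between-type variance is g²/4. The ratio of adjusted to unadjusted SE is 1/√(1 + g²/4) = 0.992, 0.970, 0.894 and 0.800 for g = 0.25, 0.5, 1.0 and 1.5 (simulated 0.992, 0.970, 0.893, 0.798).

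One cell by hand, g = 1.0, 50 per arm, difference 0.5 SD:
- True SE = √(2/50) = 0.200; SE reported by the unadjusted test = 0.200 × √1.25 = 0.2236.
- The test rejects above 1.984 × 0.2236 = 0.444, so power ≈ Φ((0.5 − 0.444)/0.200) = Φ(0.28) = 61%.
- With the stratum in the model it rejects above 1.985 × 0.200 = 0.397, so power ≈ Φ(0.515) = 70%.

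**Wound type, simulation** (20,000 runs per cell; power is unadjusted / adjusted, in %):

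| Gap g | Variance share | Type I, unadjusted, 50/arm | 0.5 SD, 50/arm | 0.75 SD, 50/arm | 0.5 SD, 40/arm | 0.75 SD, 40/arm |
|---|---|---|---|---|---|---|
| 0.25 | 1.5% | 5.0% | 69.0 / 69.5 | 95.8 / 95.9 | 59.6 / 60.0 | 91.0 / 91.1 |
| 0.5 | 6% | 4.3% | 67.7 / 69.8 | 95.3 / 95.8 | 57.5 / 59.9 | 89.9 / 91.0 |
| 1.0 | 20% | 2.7% | 60.8 / 69.3 | 93.6 / 96.0 | 50.7 / 59.8 | 86.7 / 91.1 |
| 1.5 | 36% | 1.5% | 51.1 / 70.1 | 89.3 / 95.9 | 40.7 / 59.9 | 80.3 / 91.0 |

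The variance share is (g²/4)/(1 + g²/4). Adjusted type I error stays at 4.9–5.2%. At 1.0 SD the loss is at most about 0.5 points with 50 per arm and 2 points with 40. A 30:70 mix with 50 per arm gives similar results: type I error 4.9, 4.6, 3.1 and 2.0%, and unadjusted power at 0.5 SD of 69.6, 67.5, 62.4 and 53.4%.

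**Baseline area alone** (no wound-type effect, 50 per arm). The SE ratio is √(1 − R²) = 0.949, 0.894 and 0.837 for R² = 0.1, 0.2 and 0.3 (simulated 0.954, 0.899, 0.841). Power at 0.5 SD is 73.2, 78.7 and 83.3% adjusted, against 69.3, 69.8 and 69.0% unadjusted. At 0.75 SD it is 97.5, 98.4 and 99.3%, against 96.3, 96.0 and 96.0%.

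**Both terms together, 40 per arm.** Take the difference that gives the unadjusted test 80% power (0.634 SD). Adjusted power is then 82, 84, 88, 92 and 95% for a combined R² of 0.05, 0.10, 0.20, 0.30 and 0.40. If neither variable predicts cost, simulated power goes from 79.4% to 78.8%, so the two lost degrees of freedom cost almost nothing.

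**The case against.** The test as planned is valid and errs on the conservative side, and the plan calls itself exploratory. No stated figure is contradicted.

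The true cost difference may also be large. Section 2 bases the cost argument on one product replacing two. Purely as an illustration, with similar prices and change frequencies cost would fall by about 50%, which is 0.83–1.67 SD at a CV of 0.6–0.3. At 0.83 SD with 40 per arm, power unadjusted against adjusted for wound type is 95.6 against 95.7% (gap 0.25), 94.8 against 95.4% (0.5) and 92.8 against 95.5% (1.0).

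The dramatic rows of the table need wound type to explain 20–36% of cost variance, which nothing in the plan supports. At gaps of 0.25–0.5 SD the loss at 0.5 SD is about 0.5–2 points with 50 per arm. The R² for area is equally unsourced, and because size grids are discrete and differ by product, a common linear slope is only an approximation.

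All of this stands as a limit on the size of the gain. It does not remove the case for the change. Unit prices are taken only at Last Patient Out and no expected cost difference is stated, so the plan cannot count on a large effect. Adjustment loses almost nothing if the covariates turn out to be uninformative.

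**Conclusion.** The point holds as an efficiency improvement worth considering. The cost test omits two baseline variables that the primary model already uses, one of them the stratification factor, on the only success condition decided by significance.

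The size of the loss is unknown and depends on assumed inputs. For a difference of 0.5 SD with 50 per arm, it is about 0.5–2 points of power for a wound-type gap of 0.25–0.5 SD, and about 9 points for a gap of 1.0 SD. Baseline area is the better-supported term: adjusting for it gains about 4, 9 and 14 points if it explains 10, 20 and 30% of cost variance. For a difference near 1.0 SD or larger, the choice hardly matters. The risk is a missed saving, never a spurious one.

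**What to change.** In section 10.1, analyse total cost by a linear model with treatment and wound type as fixed effects and baseline wound area as covariate. Report the adjusted difference with its 95% confidence interval, and state that the section 10.4 cost condition is judged on this model. Keep the unadjusted comparison of means as a sensitivity analysis. A robust or bootstrap interval is a reasonable option if costs are skewed, but the case does not depend on it. For consistency, add wound type to the two EQ-5D-5L models.

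A minor addition: state in one sentence how cost is handled for subjects who leave early, with a sensitivity analysis that allows for time observed and counts zero cost after healing. The plan requires withdrawn subjects to complete the termination visit (section 5.1) but gives no rule for their cost.

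No new data, visit, form or subject is needed. Because the analysis sits in the investigation plan itself, the change goes through the signed and logged amendment route of section 12. It should be made before database lock, while the trial statistician is still blinded, so that the choice of covariates cannot look selective.

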10.2. Sample size

The primary endpoint is the percent WAR from baseline to week 4. The sample size calculation assumes that the standard deviation of WAR in each group will be similar to what was estimated in the Biatain-Ag meta-analysis, namely SD=43%(13).

A sample size of 40 completing subjects in each arm will result in a study that is powered by 80% to get a width of a 95% confidence interval for the difference in mean WAR between the two treatments of less than +/-21%. This is based on an analysis of assumed normally distributed data.

Further, the width of the 95% confidence interval for the estimated mean WAR in each treatment group will with high probability (power of 89%) be less than +/- 15%.

The expected width of the confidence intervals based on a total of 80 subjects is deemed adequate to be able to compare the performance of the 2 treatments.

To account for lost to follow-up/dropout rate of 20%, 100 subjects are required for this study.

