10.3. Level of significance and power

A two-sided significance level of 5% will be applied. For information regarding the power see section 10.2.

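### The two precision probabilities in section 10.2 do not reproduce as printed and appear to be exchanged: about 89% belongs to the difference and about 80% to the single arm

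*Combined protocol and SAP*

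**What the plan says.** Section 10.2 bases the sample size on precision; it states no margin and no effect size. The SD of percentage wound area reduction (WAR) in each group is taken from a meta-analysis, "namely SD=43%(13"). Two statements follow for "A sample size of 40 completing subjects in each arm":

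- **Difference between arms:** the study is "powered by 80% to get a width of a 95% confidence interval for the difference in mean WAR between the two treatments", and the limit set for that interval is ±21 percentage points.
- **Each arm's mean:** the interval width "will with high probability (power of 89%) be less than +/- 15" percentage points.

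The section adds that the calculation assumes normal data, and it judges the interval widths "based on a total of 80 subjects" adequate for comparing the treatments. Section 10.3 gives no power of its own: "For information regarding the power see section 10.2". Section 10.1 plans to report both kinds of interval for the primary endpoint.

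**The concern.** The order of the two probabilities is suspicious before any exact calculation. The ratio of the limits, 21/15 = 1.40, is almost √2, which is the ratio of the two standard errors. Relative to the half-width expected at SD 43, the two limits are therefore about equally generous. The interval for the difference uses 78 degrees of freedom and the single-arm interval 39, so the SD behind the difference is estimated more precisely. With nearly equal headroom, the difference should have the higher probability of meeting its limit. The plan prints the reverse.

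No other quantitative statement supports 80 completers, and section 10.3 sends the reader here for power. If the figures are misplaced, the precision of the primary contrast is described as worse than it is, and that of each arm's mean may be described as better than it is. Anyone checking the section will fail to reproduce either number.

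**Working it through.** **Inputs, all from sections 10.2 and 10.3:** SD = 43 in each arm; n = 40 completers per arm (80 in total, so 1:1); 95% two-sided intervals; normal data; half-width limits 21 (difference) and 15 (single arm). Stated probabilities: 80% and 89%.

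**Formula.** The half-width is t(0.975, df) × s × √(k/n), with k = 2 for the difference and k = 1 for one arm. Let E be its value at s = 43. Because df × s²/43² follows a chi-square distribution on df degrees of freedom,

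P(half-width < h) = P(χ²(df) < df × (h/E)²).

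**Difference (stated 80%)**
- df = 78, t = 1.991, 43 × √(2/40) = 9.615, so E = 19.14.
- 78 × (21/19.14)² = 93.9.
- P(χ²(78) < 93.9) = **89.4%**.

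**Single arm (stated 89%)**
- df = 39, t = 2.023, 43/√40 = 6.799, so E = 13.75.
- 39 × (15/13.75)² = 46.4.
- P(χ²(39) < 46.4) = **80.6%**.

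**Conditional on the interval covering the true value**, a common convention for precision-based sample sizes: **89.1%** and **80.0%**. To the whole percent these are the two printed figures with places exchanged.

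**Other readings tried**

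| Reading | Difference < 21 (stated 80%) | Single arm < 15 (stated 89%) |
|---|---|---|
| t, each arm's own variance | 89.4% | 80.6% |
| Same, conditional on coverage | 89.1% | 80.0% |
| Pooled variance, df 78 | 89.4% | 91.6% |
| Pooled variance, df 76 | 89.0% | 91.3% |
| z in place of t | 92.7% | 87.7% |
| Welch interval | 89.3% | – |
| 21 and 15 read as full widths | about 0% | about 0% |
| 90% intervals | over 99% | over 99% |

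No row gives 80% and 89% in the printed places. A different SD does not help. With own-variance intervals, SDs from 41 (97.1% and 90.6%) to 45 (74.3% and 67.2%) always leave the difference with the higher probability.

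**Size of the discrepancy**
- Difference: 89.4 − 80 = 9.4 points too low. An 80% probability for ±21 needs only 38 per arm (81.0%). At 40 per arm, the half-width met with 80% probability is 20.4.
- Single arm, own variance: 89 − 80.6 = 8.4 points too high (9 against the conditional 80.0%). An 89% probability for ±15 needs 43 per arm (89.8%). At 40 per arm, the half-width met with 89% probability is 15.6.

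The dropout step is correct: 80/0.8 = 100.

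**The case against.** The strongest reply is that section 10.1 estimates each arm's mean from one model with treatment, wound type and baseline area. That model has a single residual variance on about 76 degrees of freedom, so the single-arm probability would be about 91%, and 89% would not be an overstatement. If adjusted means weight the two wound types equally and the types split 60/40, the result is 88.9%. The 80% for the difference could then be a nominal target with the limit rounded up: the half-width met with 80% probability is 20.4, and ±20 is met with only 72.9%. On that view both statements are safe, and nothing was exchanged.

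Part of this stands. The single-arm overstatement, and the 43 per arm that would cure it, apply to an interval based on that arm's own SD and not to the pooled model. The transposition is inferred from the match, because the plan shows no working. The error for the primary contrast is conservative, and no analysis or pass/fail rule uses either probability.

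The rest does not rescue the text. The pooled reading still gives 89% for the difference, not 80%. The 60/40 split with equal weighting is not in the plan. The rounding explanation covers only the first figure, so the reply needs a separate device for each number. Exchanging the two figures explains both at once.

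**Conclusion.** The concern holds. With the plan's inputs and standard t-based intervals, the probability of meeting the limit is about 89% for the difference and about 80% for each arm's mean; section 10.2 prints 80% and 89%. The figure for the primary contrast is about 9 points too low under every 95% half-width method tried that uses t. The figure for one arm is 8 to 9 points too high for an own-variance interval and about 2 points too low for a pooled one. An exchange of the two numbers is by far the most economical explanation, but it remains an inference. The result rests on SD 43, 40 completers per arm, normal data, and 21 and 15 read as half-widths.

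The consequence is limited: the sample size stands, and the primary contrast is better protected than claimed. It should still be corrected, because these are the only power figures in the plan.

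**What to change.** Restate section 10.2 along these lines: with 40 completing subjects per arm and SD 43, there is about 89% probability that the half-width of the 95% interval for the difference in mean WAR is below 21 percentage points, and about 80% probability that the half-width for each arm's mean is below 15, using that arm's own SD. Describe these as precision probabilities for half-widths instead of power for a width, and let section 10.3 refer to them in the same terms.

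If the sponsor means the pooled-variance interval from the section 10.1 model, the text should say so and give about 91% for each arm; the figure for the difference stays at about 89%.

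The cost is two figures and a few words in one section, plus the matching reference in 10.3. The 80 completers, the 100 subjects and the planned analyses are unchanged. The correction should be made before the figures are carried into the clinical investigation report.
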